Upon arrival, participants will be asked to complete some questionnaires whilst their meal is being prepared. Questionnaires include:

- All three visits
 - Level of hunger/fullness
 - Cognitive task
- Final visit
 - Follow-up questionnaire (Satiety responsiveness questionnaire, compensatory health beliefs)
 - Aim guessing/ranking meals

Participants will be provided with their lunch (loaded fries). There will be a large bowl of chips (low ED; 1.17kcal/g; medium ED; 1.74kcal/g; high ED; 3.00kcal/g), and a separate large bowl of chilli at low (1.1kcal/g), medium (1.6kcal/g) or high (3.2kcal/g) ED. Participants will serve themselves from the provided bowls. The three different chilli recipes will be made in the lab using a standardised procedure. ED will be varied by altering the ingredients used, and proportions of ingredients. A review of existing energy density manipulation studies(14) found that very similar effects were identified in studies whether the nutritional composition was altered or not, so it was deemed appropriate to alter the nutritional content of the meal. Details of all food served are shown in Table 1. These recipes will be made in bulk, frozen and labelled clearly so each portion can be defrosted and prepared for each participant on the day of consumption.

Loaded fries were chosen as the test meal, as it is a food frequently served in the out-of-home food sector, and a meal which is relatively simple to manipulate in terms of energy density. The recipes

were tested several times to ensure they were equally appetising, and sent to the SGS Cambridge Analysis Lab to ensure they contained the expected energy densities.

Throughout the study, random samples of each chilli will be sent off to the SGS Cambridge Analysis Lab to test for nutritional content of each of the products. This will ensure that nutritional components remain consistent over the course of the study. We plan to do this twice over the course of data collection.

The amount of food served will fill a large serving bowl (750g of each chilli, with 500g of chips). Participants will be left alone and asked to eat as much or as little of their meal as they would like. When they have finished their meal, participants will be told to call the researcher back in to continue the study. The plate will be taken from participants and any remaining food weighed in order to calculate total grams and energy consumed. Participants will be asked to rate sensory aspects of the meal.

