After each lunch session, participants will be provided with a snack box, and told they can eat as much or as little of what is provided as they wish.

Participants will return for an evening session to eat their dinner (4.30-6.30). They will be required to bring the snack box, and any remaining snacks with them. Here, participants will once again be asked to complete hunger and fullness scales, and a cognitive task. Following this, a 3-cheese pasta ready meal (800g) with a side of mixed vegetables (225g) will be provided for participants to serve themselves. Once participants have eaten all they wish to of the pasta meal, dessert will be provided (brownie bites and flapjack bites) which once again, they can help themselves to as much or as little as they would like.

After their final study dinner, participants will be given a follow-up questionnaire to assess compensatory health beliefs and satiety responsiveness. They will also be asked to guess the aim of the study and rank the foods they have eaten for each lunch session in terms of healthiness. Following this they will be fully debriefed.

Table 1: All test foods

	Low ED			Medium ED			High ED		
	g	kcal	£	g	kcal	£	g	kcal	£
LUNCH									
Potatoes	500	585	£1.27	500	870	£0.97	500	1500	£2.16
Chilli	750	885	£3.17	750	1275	£3.14	750	2430	£3.92
Water	500	0	£0.00	500	0	£0.00	500	0	£0.00
DINNER									
Ready meal	800	1164	£3.50	800	1164	£3.50	800	1164	£3.50
Mixed vegetables	225	84	£1.50	225	84	£1.50	225	84	£1.50
Water	500	0	£0.00	500	0	£0.00	500	0	£0.00
DESSERT									
Brownie bites	220	860	£2.25	220	860	£2.25	220	860	£2.25
Flapjack bites	280	1260	£2.25	280	1260	£2.25	280	1260	£2.25
Water	500	0	£0.00	500	0	£0.00	500	0	£0.00
SNACKBOX									
Apple	268	142.04	£0.80	268	142.04	£0.80	268	142.04	£0.80
Cereal bar	60	232.8	£0.67	60	232.8	£0.67	60	232.8	£0.67
Crisps	50	270	£0.18	50	270	£0.18	50	270	£0.18
Carrot batons	100	43	£0.58	100	43	£0.58	100	43	£0.58

Biscuits	22	104.72	£0.17	22	104.72	£0.17	22	104.72	£0.17
Dried fruit and nut mix	25	133	£0.55	25	133	£0.55	25	133	£0.55
Chilli									
Mince (5%/15%/20%)	250		£1.43	313		£1.82	769		£2.75
Onion	75		£0.04	68		£0.03	12		£0.01
Carrot	100		£0.05	52		£0.03	6		£0.01
Mushroom	100		£0.30	52		£0.16	6		£0.02
Tomato	100		£0.27	52		£0.14	6		£0.02

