A subjective measure of their socioeconomic position using the MacArthur Scale of Subjective Social Status (SSS) (19). SSS will be recorded as this measure has been found to have strong associations with overweight and obesity(20).

Childhood SES(21): for this measure, participants will be asked to provide the educational attainment and occupation of each primary caregiver at the time the individual was 8-10 years old. Parental educational attainment will be reported in 6 categories, if there are two caregivers, the average will be calculated.

- 1 = less than high school
- 2 = high school
- 3 = 2-year degree
- 4 = 4-year degree
- 5 = master's degree
- 6 = doctorate/professional degree

Parental occupation will be coded independently by two researchers using Hollingshead's 9-point scale(22), and inter-rater reliability assessed.

Sensory ratings (Appendix E)

Participants will be asked to complete sensory ratings once they have finished their meal for:

- Pleasant
- Sweet
- Savoury
- Salty
- Familiar
- Filling
- Soft
- Appetising (visually)

All will be presented on visual analogue scales ranging from 1-100 anchored by "not at all" and "extremely" respectively.

Measure of hunger/fullness

Situational levels of hunger and fullness will be obtained before and after lunch and dinner by using visual analogue scales ranging from 1-100 anchored by “not at all” and “extremely” respectively.

Satiety responsiveness (Appendix F)

Participants will complete a satiety responsiveness subscale of the Adult Eating Behaviour Questionnaire (AEBQ)(23)

Compensatory health beliefs (Appendix G)

Participants will complete a compensatory health beliefs questionnaire. This will be made up of 8 items, from the exercise and portion size subscales from the diet-related Compensatory Health Beliefs Scale (Diet-CHBS)(24). Participants are required to rate all items from 1 (not at all) to 5 (very much) for how much the compensatory health belief matches their own beliefs e.g. “To maintain your weight, it is fine to eat a high caloric snack in between meals, if you compensate for this by eating a smaller portion later in the day”.

Food diary

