At each lunch session, participants will be asked to report any foods or beverages (excluding water) consumed the morning of the study, to ensure nothing was consumed in the two hours prior to the study, and to ensure breakfast is similar across the three sessions. At each dinner session, participants will be asked to report any foods or beverages (excluding water) consumed that were not provided by the researchers.

Aim guessing (Appendix H)

At the end of their final visit, participants will be asked what they believe the aims of the study to be. Anyone that guesses the study aims to be investigating the influence of energy density on intake (e.g. the healthiness/energy content of meal on how much was consumed at lunch time or at dinner time) will be coded as being aware of study aims. One researcher will code awareness of aims and a second researcher will independently verify.

Participants will then be asked to rank the three lunch time meals in terms of level of energy density.

Additional tasks

Additional tasks will be completed to account for the study description of ‘A study of diet on cognitive function’. Before and after each lunch and dinner meal, participants will complete a Stroop task.

Study flow

	Visit 1	Visit 2	Visit 3
RECRUITMENT	Participants who could not take part in the previous mood, diet and sleep study will be contacted to take part in this study (Appendix A)		

SCREENING	
Participants will come into the lab to be screened. This will involve:
 
Medical history questionnaire
 
Baseline demographic questionnaire (Appendix B)
 
Height and weight measurement
 
Ensuring they like all test foods.
		
INFORMED CONSENT	
Participants will be asked to read the information sheet (Appendix C).
 
Participants who want to proceed will read the consent form and tick a box providing their consent (Appendix D).
		
RANDOMISATION	Before their first session, the order that meals are presented to participants will be randomized.		
BASELINE ASSESSMENTS (Inquisit)	Participants will complete a baseline demographic questionnaire, measures of hunger and fullness, and a cognitive task	Participants will complete measures of hunger and fullness and a cognitive task	Participants will complete measures of hunger and fullness and a cognitive task

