DINNER	
After completing hunger and fullness ratings and a cognitive task again, participants will be provided with a glass of water and a ready-meal for dinner, which they can serve themselves.
 
After dinner, participants will be provided with a dessert to have as much or as little of as they like.
	
After completing hunger and fullness ratings and a cognitive task again, participants will be provided with a glass of water and a ready-meal for dinner, which they can serve themselves.
 
After dinner, participants will be provided with a dessert to have as much or as little of as they like.
	
After completing hunger and fullness ratings and a cognitive task again, participants will be provided with a glass of water and a ready-meal for dinner, which they can serve themselves.
 
After dinner, participants will be provided with a dessert to have as much or as little of as they like.

POST-MEAL	Participants will complete hunger and fullness ratings and a cognitive task again.	Participants will complete hunger and fullness ratings and a cognitive task again.	Participants will complete hunger and fullness ratings and a cognitive task again. Participants will complete measures of satiety responsiveness (Appendix F) and compensatory health beliefs (Appendix G).
DEBRIEFING			Aim guessing in an open-ended response format will be provided to participants (Appendix H). Following this, participants will be asked to rank the meals from the three weeks in order of energy density. Participants will be debriefed on study aims (Appendix H).
DATA MANAGEMENT	
The result files will contain:
 
 ○ Participant unique ID (randomly generated) ○ Demographic and questionnaire data ○ Amount of each lunch meal consumed (g) ○ Energy consumed for each lunch (kcal) ○ Snacks consumed ○ Amount of dinner and dessert consumed (g) ○ Energy consumed for dinner and dessert (kcal) 		

Analysis Plan

Participant characteristics:

Only participants who have completed the entire study (all three visits) will be included in analysis. We will report analyses with any participants who guess the aims of the study included and excluded.

If any participants do not follow study instructions (e.g. do not consumer any or only a very small amount of any of the food (<50kcal) then they will be removed from primary analyses.

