Appendix G: Compensatory Health Beliefs

		Strongly disagree 1	Disagree 2	Neither agree nor disagree 3	Agree 4	Strongly agree 5
1.	To maintain your weight, it is fine to do less exercise if you eat small portions					
2.	To maintain your weight, it is fine to have less exercise if you eat products with a front-of-package logo					
3.	When I eat less, it's not necessary to have a lot of exercise					
4.	When I mainly eat products with a front-of-package logo, it is not necessary to have a lot of exercise					
5.	If I eat a small meal, it's fine to have a larger portion during the next meal					
6.	To maintain your weight, it is fine to eat a large meal, if you eat a small portion during the next meal					
7.	To maintain your weight, it is fine to eat a high caloric snack in between meals, if you compensate for this by eating a smaller portion later in the day					
8.	If I eat a small meal, there is no harm in eating more cookies and candies					

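### At Visit 3 the open-ended aim question follows scales that echo the concealed aim, so some participants who were unaware while eating may be coded as aware and needlessly dropped from the aim-guesser-excluded analysis

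*Combined protocol and SAP*

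**What the plan says.** The Study flow table, Visit 3, POST-MEAL row, reads "Participants will complete measures of satiety responsiveness (Appendix F) and compensatory health beliefs (Appendix G". The DEBRIEFING row below it reads "Aim guessing in an open-ended response format will be provided to participants (Appendix H", followed by the meal ranking and the debrief itself.

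The Procedure text gives the same sequence: "After their final study dinner, participants will be given a follow-up questionnaire to assess compensatory health beliefs and satiety responsiveness", and then "They will also be asked to guess the aim of the study and rank the foods they have eaten for each lunch session".

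Earlier in the Procedure, the list of questionnaires completed on arrival, while the meal is prepared, has a final-visit entry. It contains "Follow-up questionnaire (Satiety responsiveness questionnaire, compensatory health beliefs" together with aim guessing and meal ranking.

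On content, the measures section says of the beliefs questionnaire: "This will be made up of 8 items, from the exercise and portion size subscales from the diet-related Compensatory Health Beliefs Scale (Diet-CHBS". Appendix G item 6, for example, is "To maintain your weight, it is fine to eat a large meal, if you eat a small portion during the next meal".

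On coding, the Aim guessing section says "Anyone that guesses the study aims to be investigating the influence of energy density on intake" is to be coded as aware. Its example is a guess that the healthiness or energy content of a meal affects how much is eaten at lunch or dinner. The Analysis Plan then reports analyses both with and without these participants.

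**The concern.** An awareness probe is useful if it captures what participants suspected while they were eating. Here it is put to them minutes after items about eating less at one occasion to make up for another, and nothing earlier in the study records what they suspected. Someone who accepted the cognitive-function cover story through all three visits could build a codable answer from the questionnaire just completed. Awareness created at that point cannot have influenced intake, because all intake has been measured by then. The coding rule still treats it in the same way as suspicion formed at lunch. Double checking of the coding by a second researcher does not separate the two, since both would read the same cued answer.

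What is at stake is the comparison of results with and without aim guessers, which is the plan's check on whether awareness influenced intake.

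**Working it through.** **Order and content, set side by side**

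- Sequence: the Study flow and the Procedure narrative agree that both scales come before the aim question. They differ only on which scale is named first (satiety first in the table, beliefs first in the narrative), so the four satiety items may or may not fall between the beliefs items and the aim question.
- Content: Appendix G items 1 to 4 concern exercise. Items 5 to 7 concern a smaller or larger portion at one occasion balanced against another; item 8 concerns sweet foods after a small meal. Only item 7 refers to calories.
- Concealed aim: the debriefing text (Appendix I) tells participants that the study looked for compensation through a smaller dinner after a less healthy lunch. Items 6 and 7 come close to this.
- Coding rule: it turns on what is guessed and is silent on when the suspicion arose.
- Direction of error: cueing can only add people to the aware group. Those who would have guessed anyway are still coded as aware.

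**What over-classification could cost the excluded analysis**

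Inputs from the Sample size section: d = 0.52, minimum n = 32, power printed as 0.8% and read as 80%. The significance levels are 0.05 (primary) and 0.01 (secondary). Two-sided testing is assumed, as sidedness is not stated.

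Formula: for n pairs, the test statistic follows a noncentral t distribution with n − 1 degrees of freedom and noncentrality d√n. Power is the probability that it falls beyond ± the central-t critical value.

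Plan's own figure: the smallest n with power of at least 0.80 at d = 0.52 and α = 0.05 is 32 (power 0.813). The stated sample size is reproduced.

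Now let k of the 32 be excluded as aware, for whatever reason, with d held at 0.52:

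| k | n = 32 − k | 0.52 × √n | Power, α = 0.05 | Power, α = 0.01 |
|---|---|---|---|---|
| 0 | 32 | 2.94 | 0.81 | 0.58 |
| 3 | 29 | 2.80 | 0.77 | 0.52 |
| 6 | 26 | 2.65 | 0.72 | 0.46 |
| 10 | 22 | 2.44 | 0.64 | 0.37 |

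The range for k is an assumption: 3 to 10 is roughly 10% to 30% of 32 (3.2 to 9.6). The documents give neither an awareness rate nor a cueing rate.

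**The case against.** The strongest reply is that over-classification does not defeat the check. A reader might infer that the excluded analysis can no longer serve as a test of awareness effects. The documents do not support that: true guessers are still removed, so the remaining sample is still unaware, only smaller and possibly selected if people who are readily cued differ from the rest. This reply stands, and it limits the harm to precision and some selection.

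A reader might also infer that participants are lost from the main results. They are not: the Analysis Plan reports both versions, and no intake value depends on the classification.

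The overlap between scale and coding rule is partial. A participant cued to answer portion size, exercise or beliefs about compensation would not clearly meet a rule about energy density, healthiness or energy content. Other cues exist too: the recruitment text announces three variations of the lunch, and hunger and sensory ratings are repeated at every visit. These points make the amount of cueing uncertain. They do not remove the problem, because the other cues arise before or during the period in which intake is measured, so suspicion from them is the kind that the probe ought to detect.

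Finally, the arrival list could be read to mean that the third session's eating would itself be primed. The rest of the Procedure, the Aim guessing section and the Study flow all place these items at the end of the final visit, so the list is a drafting conflict to correct and not evidence of priming.

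**Conclusion.** The point holds as a modest weakness in one pre-specified comparison. The order of the instruments and the coding rule allow awareness created after all eating is finished to count as awareness of the aims. The likely effect is that the analysis without aim guessers loses some participants for no reason.

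Lost power could then be mistaken for a changed finding. The Analysis Plan judges sensitivity analyses by whether results cross the significance threshold. The aim-guesser comparison is not listed under that heading, but it is likely to be read in the same way.

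The size is not known. If exclusions rose from 3 to 10 of 32, power at d = 0.52 would fall from about 0.77 to 0.64 at the 0.05 level and from 0.52 to 0.37 at the 0.01 level. This rests on assumed exclusion counts, two-sided testing, 32 completers and an unchanged effect size. That cueing will occur is a reasoned expectation; the documents do not demonstrate it.

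**What to change.** At Visit 3, after the final dinner and the post-meal ratings and cognitive task, use this order:

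1. Open-ended aim question, with no revision of the answer afterwards.
2. Appendices F and G.
3. Meal ranking.
4. Debrief.

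Change the Procedure narrative and the Study flow table to match. Take the final-visit entries out of the Procedure's list of arrival questionnaires, so that it agrees with the Aim guessing section and the Study flow.

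The cost is a reordering of forms and a few lines of text; the sample size and the analyses stay as they are. It is not entirely free. Being asked about the aim could slightly colour the scale answers, and the debriefing text says the scales will be used to test characteristics that may affect intake, so they cannot be treated as purely descriptive. The open question discloses nothing about the aim, and keeping the ranking after the scales limits this risk.

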Is there any additional blinding in this study? To attempt to reduce the likelihood of aim guessing, participants will be recruited to a study labelled as 'a study of diet on cognitive function'.

Study design: An experimental, within-subjects design. Participants will be asked to visit the lab for three consecutive weeks to complete some questionnaires and eat meals at lunch time and dinner time. Participants will complete all three conditions – low energy density, medium energy density and high energy density meals which will be eaten ad-libitum. Participants will be provided with a box of snacks to eat throughout the day if they wish to, and will return to the lab for dinner, where they will be served an ad-libitum meal and a dessert.

Randomization: Participants will complete all three conditions. The order the conditions are presented to participants will be randomised prior to arrival.

Sampling Plan

Existing Data: Registration prior to creation of data

Explanation of existing data: N/A

Data collection procedures: Participant database. If required, participants will also be recruited from the local community (e.g. adverts on social media/posters in the university)

Inclusion criteria:

- Currently reside in the UK
- Over the age of 18 years
- Fluent English speaker
- Like the test foods
- Have a BMI between the ranges of 18.5 and 35.

Exclusion criteria:

- Pregnant/breastfeeding
- Partaking in a fast or other restrictive eating for religious reasons at time of participation

- Currently following a diet
- On medication that affects appetite
- Being a smoker
- Current or historic eating disorder
- Dietary restrictions/intolerances including:
 - Any allergies
 - Vegan/vegetarian
 - Gluten-free
 - Dairy-free
 - Sugar-free

Procedure:

Once signed up, participants will attend a short screening session, where they will be asked to complete a medical history questionnaire, a baseline demographic questionnaire, have their height and weight measured, and check they like the test foods on offer.

Participants will be told upon registration that they should have the same breakfast the morning of each session. Arrangements will be made for the participants to arrive at the lab around the time they would usually eat their lunch (11.30-2.30) and be allocated to one of the following groups for each session (order randomised):

- Low energy density lunch
- Medium energy density lunch
- High energy density lunch

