Participant characteristics will be presented in a table. Data will include age, gender, ethnicity, BMI, highest education level, perceived social status, childhood SEP, compensatory health beliefs and satiety awareness. Continuous variables will be summarised by means and standard deviations, categorical variables will be summarised by counts and percentages.

Primary analyses:

Two repeated-measures, within-subjects ANOVAs will assess lunchtime (manipulated meal) kcal and gram intake across the three conditions. Where significant main effects are identified, post-hoc pairwise comparisons will be performed to identify where these differences exist. Sensory ratings of the three meals will be compared using repeated-measures, within-subjects ANOVAs to assess whether all meals were rated equally. Results will be considered statistically significant at $p<0.05$.

Secondary analyses:

Two repeated-measures, within-subjects ANOVAs will assess later kcal and gram intake (dinner, dessert and snacks) across the three conditions (low ED, medium ED and high ED). Where significant main effects are identified, post-hoc analyses will be performed to identify where these differences exist.

A repeated-measures, within-subjects ANOVA will assess daily energy intake (sum of lunch, dinner, dessert, snacks and additional food) across the three conditions. Where significant main effects are identified, post-hoc analyses will be performed to identify where these differences exist.

To account for multiple comparisons, results for secondary analyses will be considered significant at $p<.01$.

Sensitivity analyses:

We will examine evidence of extreme outliers (+3 standard deviations from the session mean) in grams consumed for each test food, and for any outcomes identified as outliers we will examine the effect of winsorizing the outlier.

If we find evidence that meals differ in sensory ratings then we will also examine if results remain the same when sensory ratings are controlled for in analyses as a covariate.

We will also examine if results remain the same among participants who accurately identify the differences in energy density between foods vs. participants who do not. Alternatively, if only a small number of participants are unable to identify the correct order of energy density then we will examine if results remain the same when excluded.

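### The primary lunch analyses use condition alone and discard every lunch of a participant with incomplete data; visit, pre-lunch hunger and those lunches could be used for modest precision at little cost

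*Combined protocol and SAP*

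**What the plan says.** **Model.** Under Analysis Plan, Primary analyses: "Two repeated-measures, within-subjects ANOVAs will assess lunchtime (manipulated meal) kcal and gram intake across the three conditions". Significant main effects are followed by pairwise comparisons. The only covariate named anywhere in the Analysis Plan is the sensory ratings, and only in a conditional sensitivity analysis.

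**Order.** Under Design Plan, Randomization: "The order the conditions are presented to participants will be randomised prior to arrival". No balancing of the sequences is described.

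**Hunger.** Under Measure of hunger/fullness: "Situational levels of hunger and fullness will be obtained before and after lunch and dinner". The Study flow table repeats this for the later visits, before lunch: "Participants will complete measures of hunger and fullness and a cognitive task". No primary, secondary or sensitivity analysis uses the rating.

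**Standardisation before lunch.** Under Procedure: "Participants will be told upon registration that they should have the same breakfast the morning of each session". The Food diary is meant "to ensure nothing was consumed in the two hours prior to the study, and to ensure breakfast is similar across the three sessions".

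**Who is analysed.** "Only participants who have completed the entire study (all three visits) will be included in analysis". The Data exclusion and Missing data entries remove dropouts, and participants with missing data, altogether. A further rule covers people who do not follow instructions, for example by eating none or very little of "any of the food (<50kcal) then they will be removed from primary analyses".

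**Sample size.** The post-hoc t-tests at d=0.52 are said to need 32 participants, and 32 is also the recruitment minimum.

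**The concern.** This is a three-visit crossover with two sources of within-person variation that are already recorded: visit number and hunger on arrival. Hunger rated before lunch cannot be altered by that day's lunch, so it is a legitimate covariate. Leaving both in the error term can widen the pairwise comparisons, and those comparisons carry the hypotheses (grams similar from low to medium energy density, lower from medium to high).

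The deletion rules add to this. Someone who misses the third visit has already eaten two weighed lunches, which give a complete within-person comparison of two conditions. The plan throws that away, although the calculated sample size has almost no slack.

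**Working it through.** **1. The plan's own figure.** Inputs from Sample size: d=0.52 and 80% power (printed as 0.8%). Two-sided 5% is assumed, since sidedness is not stated. For a paired t-test with n participants, the noncentrality is d√n on n−1 degrees of freedom. At n=32 it is 0.52 × √32 = 2.94.

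| Analysed participants | Power |
|---|---|
| 32 | 81.3% |
| 31 | 79.997% |
| 30 | 78.6% |
| 29 | 77.1% |
| 27 | 73.9% |

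The plan's 32 reproduces exactly. One deletion takes power marginally below 80%, and two take it to 78.6%.

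**2. Visit and hunger terms.** The documents give no visit drift and no hunger correlation, so these are assumptions. Simulated omnibus power, N=32, complete data, a 0.52 SD effect, and a model with participant effects:

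| Setting | Condition only | With visit and hunger |
|---|---|---|
| Balanced blocks, neither matters | 85.2% | 85.1% |
| Simple randomisation, neither matters | 84.7% | 82.8% |
| Simple randomisation, drift 0.2 SD per visit | 83.0% | 84.4% |
| Simple randomisation, drift 0.3 and hunger slope 0.3 (optimistic end) | 71.6% | 83.1% |

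In a separate null simulation with random order, type I error was 5.0–5.3% without a visit term and 4.8–5.3% with one, at drifts of 0 to 0.5 SD of the paired difference. Omitting visit is therefore not a validity problem.

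**3. Keeping lunches when visits are missed.** No dropout rate is given. Assume 32 recruited, within-person correlation 0.5, and visit 3 missing completely at random. Post-hoc power from paired t-tests with no drift:

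- 3 people affected: 77.1% with completers only, 78.5% with all available pairs.
- 5 people affected: 74.1% and 76.5%.

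Retention alone is thus worth 1.4 to 2.4 points.

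**4. Choice of covariance.** Kcal is grams times energy density. Weighting chips (1.17, 1.74, 3.00 kcal/g) at 500 g and the tabulated chilli values (1.14, 1.56, 3.24 kcal/g) at 750 g:

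- Low: (585 + 855)/1250 = 1.152 kcal/g
- Medium: (870 + 1170)/1250 = 1.632 kcal/g
- High: (1500 + 2430)/1250 = 3.144 kcal/g

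If gram SDs are equal, kcal SDs differ in these proportions. A random-intercept model with one pooled error term then gives, on complete data, the same kcal F as the uncorrected ANOVA. That F rejects 6.6% of the time under the null, against 5.0% with Greenhouse-Geisser. Pooled-error kcal pairs would be tested at 0.2% (low-medium), 9.2% (low-high) and 8.6% (medium-high) instead of 5%. For grams, the pooled low-medium contrast reaches 6.4–7.3% if the high-density SD is 0.8–0.6 of the others. Each contrast therefore needs its own variance.

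**5. Price of an unstructured covariance.** With complete data and condition only, the omnibus becomes an F on 2 and 30 degrees of freedom instead of 2 and 62. Take f=0.25, correlation 0.5 and sphericity. The noncentrality is 32 × 3 × 0.25² / 0.5 = 12. Power is 86.6% for the ANOVA and 84.7% for the unstructured model, a cost of about 2 points. Pairwise tests then coincide with paired t-tests, so they lose nothing.

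**The case against.** The strongest case is that the planned analysis is already sound. Randomised order protects the condition comparison, the common breakfast and two-hour food check should limit variation in hunger, and any gain depends on drift and correlations that nobody has stated. All of that stands. It is why this is a precision point, and why the hunger gain is probably small.

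A mixed model can also do harm. With a pooled error term it would replace paired t-tests that hold 5% by contrasts that may not. That objection is right, and it is met by the unstructured covariance and by keeping the planned tests alongside.

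Two stronger readings are tempting and are not supported:

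- *A reader might infer that omitting visit biases the condition effect or inflates type I error.* Order is randomised, and the simulated error rate stays near 5%.
- *A reader might infer that the study is too small and must enrol more.* The calculated 32 does deliver its stated post-hoc power, and it is worded as a minimum, so recruiting more is already allowed. The plan does not anticipate missing data among people who complete all sessions, and it does not say which missing variables trigger exclusion.

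What remains is that the plan makes no provision for missed visits other than deletion.

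**Conclusion.** The concern holds as an inexpensive improvement. The planned test is valid. It leaves recorded information unused and discards completed lunches when the pairwise tests have almost no margin: 79.997% power at 31 and 78.6% at 30.

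The size of the gain cannot be derived from the documents. For the visit and hunger terms it runs from near zero, or a loss of up to about 2 points, if neither matters, to several points under moderate assumed effects; the 11.5-point gain (71.6% to 83.1%) belongs to the optimistic end only. Retaining lunches adds 1.4 to 2.4 points if 3 to 5 people miss visit 3 completely at random. These ranges assume N=32. The retention figures also assume correlation 0.5, and the adjustment figures come from a model with a common error variance. The full adjusted model with unstructured covariance was not simulated.

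**What to change.** Prespecify the following.

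1. Allocate order in balanced blocks of the six sequences.
2. Analyse lunch grams and lunch kcal each with a linear mixed model (REML, Kenward-Roger), with condition, visit (categorical, 1–3) and that visit's pre-lunch hunger as fixed effects. Use all completed lunches, including those of participants who miss a visit. Participants removed under the study-instruction/<50 kcal rule stay removed. If any hunger rating is missing, fit without the hunger term so that no lunch is dropped.
3. Use an unstructured 3×3 covariance across conditions for both outcomes, not a random intercept with one pooled error term. Take the pairwise comparisons from this model.
4. Report the planned completer ANOVA, with Greenhouse-Geisser correction, and its paired t-tests as a sensitivity analysis.
5. State that 32 analysed participants are needed for 80% post-hoc power at d=0.52, and report the achieved power if fewer are analysed.

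**Cost.** SAP wording, a randomisation list and a somewhat more complex model; no new measurements. If visit and hunger explain nothing, omnibus power falls by up to about 2 points under simple randomisation and by almost nothing with balanced blocks. The unstructured covariance costs about 2 further omnibus points if sphericity in fact holds. Retained lunches bring the usual missing-at-random assumption, which the completer analysis helps to check.
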